Appendix 1 List of Stand-Alone Documents Not Included in the Protocol

- 1. MabThera Patient Alert Card Text for Non-Oncology Indications
- 2. Medical Record Abstraction Form Draft
- 3. Patient Questionnaire Draft
- 4. ENCePP Checklist for Study Protocols

1. MabThera Patient Alert Card Text for Non-Oncology Indications

MabThera Alert Card for patients with non-oncology diseases

Why have I been given this card?

This medicine may make you more likely to get infections. This card tells you:

- What you need to know before having MabThera
- What the signs of an infection are
- What to do if you think you might

be getting an infection.

It also includes your name and doctor's name and phone number on the back.

What should I do with this card?

- Keep this card with you all the time - such as in your wallet or purse.
- Show this card to any doctor,
 nurse or dentist you see not just
 the specialist who prescribes your
 MabThera.

Keep this card with you for 2 years

after your last dose of MabThera.

What else do I need to know?

Rarely MabThera can cause a serious brain infection, called "Progressive Multifocal Leukoencephalopathy" or PML. This can be fatal.

- Signs of PML include:
- Confusion, memory loss or problems

thinking

- Loss of balance or a change in the way you walk or talk
- Decreased strength or weakness on one side of your body
- Blurred vision or loss of vision.

If you get any of these, tell a doctor or nurse straight away. You should also tell them about your MabThera treatment.

Where can I get more information?

See the MabThera package leaflet for more information.

Treatment start date and contact details

Date of most recent infusion:
Date of first infusion:
Patient's Name:
Doctor's Name:

Doctor's contact details:

This is because side effects can develop several months after you have had treatment.

When should I not have MabThera?

Do not have MabThera if you have an active infection or a serious problem with your immune system.

Tell your doctor or nurse if you are taking or have previously taken medicines which may affect your immune system this includes chemo-therapy.

What are the signs of getting an infection?

Look out for the following possible signs of infection:

- Fever or cough all the time
- Weight loss
- Pain without injuring yourself
- Feeling generally unwell or listless.

If you get any of these, tell a doctor or nurse straight away.

You should also tell them about your

MabThera treatment.

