Q12b. Patients should show their patient alert card to any doctor, nurse or dentist involved in their treatment, not just their prescribing specialist physician.	□ Yes*	□ No	☐ I don't know
Q12d. Patients should have a list of all their medicines with them at any visit to a health care professional.	□ Yes*	□ No	☐ I don't know

Q13.	One of the side effects of using MabThera (rituximab) is immune system suppression (a lowering of your body's defenses against infections). How long after stopping MabThera (rituximab) can immune system suppression last? (Select the one most correct answer.)
	☐ A few days
	☐ Several months*
	☐ Two or more years
	□ None of the above
	☐ I don't know

Patient Alert Card Receipt and Review

Now we are going to ask you some questions about the Patient Alert Card that you may have received from your doctor or health care professional. This small, pocket-sized card contains important safety information about MabThera (rituximab).

Q14.	Have you ever received or been given a Patient Alert Card for MabThera (rituximab)?
	☐ Yes → Continue with Question 15
	□ No → Skip to Question 25
	☐ I don't know → Skip to Question 25
	er questions 15-24 only if you have received a Patient Alert Card for hera (rituximab). Otherwise, skip to question 25.
Q15.	How often have you received or been given a Patient Alert Card for MabThera (rituximab)?
	☐ Every time I receive a MabThera infusion
	☐ Some of the times I receive a MabThera infusion
	☐ Only the first time I received a MabThera infusion☐ I don't know
Q16.	Did you have the Patient Alert Card for MabThera (rituximab) with you when you arrived at the centre today? ☐ Yes ☐ No ☐ I'm not sure
Q17.	How much of the time do you keep the Patient Alert Card(s) for MabThera (rituximab) with you? (Select one answer.) All the time Some of the time None of the time I don't know
Q18.	Have you ever read the Patient Alert Card for MabThera (rituximab)? ☐ Yes → Skip to Question 20 ☐ No → Continue with Question 19 ☐ I'm not sure → Continue with Question 19

Q19.	Is there a reason why you have not read the Patient Alert Card for MabThera (rituximab)? (Select all that apply.) Someone else explained it to me I lost the Patient Alert Card I already knew the information I sometimes do not read the materials given to me by my doctor Other

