Q20.	Has someone else, other than the doctor who prescribed MabThera (rituximab) for you, explained the information in the Patient Alert Card for MabThera (rituximab) to you? (Select all that apply.) Yes, a doctor or nurse Yes, a chemist/pharmacist or someone at the chemists/pharmacy² Yes, a friend or family member Yes, a professional caregiver No I don't know
Q21.	What information should patients record on the Patient Alert Card for MabThera (rituximab)? (Select all that apply.) Start date and most recent date of MabThera (rituximab) infusion* Patient's name* Doctor's name and phone number* All of the above* None of the above I don't know
Q22.	How long should patients keep the Patient Alert Card for MabThera (rituximab) after their last dose? (Select the one most correct answer.) 1 week 24 months* 5 years None of the above I don't know

² Use "chemists" for UK and "pharmacy" for other countries.

Q23.	Since starting treatment with MabThera (rituximab), have you seen any doctors for other conditions? ☐ Yes → Continue with Question 24 ☐ No → Skip to Question 25 ☐ I don't know → Skip to Question 25
Q24.	Have you shown the Patient Alert Card for MabThera (rituximab) to doctors treating you for other conditions? ☐ Yes ☐ No ☐ I don't know
Q25.	Have you ever received or been given the package leaflet for MabThera (rituximab)? (Select all that apply.) ☐ Yes → Continue with Question 26 ☐ No → Skip to Question 28 ☐ I don't know → Skip to Question 28
Q26.	Did you have the package leaflet for MabThera (rituximab) with you when you arrived at the centre today? ☐ Yes ☐ No ☐ I don't know
Q27.	How much of the time do you keep the package leaflet(s) for MabThera (rituximab) with you? (Select one answer.) ☐ All the time ☐ Some of the time ☐ None of the time ☐ I don't know
Q28.	Have you ever received or been given other materials that describe the potential risks of receiving MabThera (rituximab)? ☐ Yes ☐ No ☐ I don't know
Q29.	Have you ever experienced an infection while undergoing treatment with MabThera (rituximab)? ☐ Yes → Continue with Question 30 ☐ No → Skip to Question 32 ☐ I don't know → Skip to Question 32

Q30.	Please indicate the most recent infection you experienced while undergoing treatment with MabThera (rituximab)?
	☐ Progressive multifocal leukoencephalopathy (PML)
	☐ Other, please specify:
	☐ I don't know

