Q31.	Which of the following actions did you take when you experienced the most recent infection while undergoing treatment with MabThera (rituximab)? (Select all that apply.)
	☐ When I noticed symptoms, I talked to my doctor
	☐ I referred to my Patient Alert Card
	☐ I told the doctor who treated me for the infection that I was taking MabThera (rituximab)
	☐ I showed the doctor who treated me for the infection the Patient Alert Card for MabThera (rituximab)
	□ None of the above
	☐ I did something not listed here. Please specify:
	☐ I don't know
Q32.	Did you look at the MabThera (rituximab) Patient Alert Card or package leaflet just before or while you were completing this questionnaire? ☐ Yes
	□ No

Demographics

In this last section, please tell us a little information about yourself to help us describe the participants completing this questionnaire.

Q33.	How old are you?
	☐ 18-25 years
	☐ 26-35 years
	☐ 36-45 years
	☐ 46-55 years
	☐ 56-65 years
	☐ 66-75 years
	☐ 76-85 years
	□ > 85 years
Q34.	Are you?
	. □ Male
	☐ Female
Q35.	What is the highest level of education you have completed? (Select one.) ³
	☐ Secondary/high school
	☐ Professional qualifications (for example, nursing, teaching, accountancy)
	☐ Other vocational/work-related qualifications gained at college or in
	employment
	☐ University – Bachelor's degree
	☐ University – Master's degree
	☐ Professional degree (e.g., MD, LLB)
	□ Doctorate degree (e.g., PhD)

Thank you again for taking time to participate in this study! Your answers are very important. If you have any questions about the safety of treatment with MabThera (rituximab), you should talk with your doctor or nurse.

Please place your completed questionnaire in the envelope provided to you by the nurse or doctor and seal the envelope. Also, be sure and let them know that you have finished.

³ Response choices apply to the UK and may need to be adapted for other countries.

5. ENCePP Checklist for Study Protocols

Doc.Ref. EMEA/540136/2009

European Network of Centres for Pharmacoep dem ology and Pharmacovigilance

ENCePP Checklist for Study Protocols (Revision 2, amended)

Adopted by the ENCePP Steering Group on 14/01/2013

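### For two of the card's instructions, showing it to any clinician and reporting symptoms straight away, behaviour items Q23, Q24 and Q31 are narrower than the card

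*Protocol*

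**What the plan says.** The card text in Appendix 1 gives two instructions that matter here.

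- **Whom to show it to:** "Show this card to any doctor", and equally any "nurse or dentist you see not just" the prescribing specialist.
- **What to do about signs of infection or PML:** "If you get any of these, tell a doctor or nurse straight away".

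The questionnaire tests both as knowledge. Q12b repeats the full list: "doctor, nurse or dentist involved in their treatment, not just their prescribing specialist physician". Q11 covers promptness.

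The behaviour items read differently.

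- Q23 asks card holders whether, since starting MabThera, "have you seen any doctors for other conditions". No or don't know skips to Q25.
- Q24 then asks "Have you shown the Patient Alert Card for MabThera (rituximab) to doctors treating you for other conditions", answered Yes, No or don't know.
- Q31 is for patients who report an infection and concerns the most recent one. Its options include "When I noticed symptoms, I talked to my doctor" and "I showed the doctor who treated me for the infection the Patient Alert Card".

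Section 8.3 lists patient actions triggered by the card as a survey variable. One example is showing the card to a doctor outside the MabThera treatment. FUM 71.1, quoted in Section 6.2, asks for the proportions of patients who use the card and who use it correctly. Specific aim 2 includes whether distributing the card may influence what patients do.

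**The concern.** An item meant to show whether patients act on an instruction should cover the same people and the same act as the instruction. Here the knowledge items match the card and the behaviour items do not. The survey could report how many patients know they should show the card to a dentist or nurse, and have no response option recording whether they did.

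At stake is one part of aim 2 and of the regulator's request: the proportion of patients who show the card as told, and who report symptoms as told. Section 8.6 says the results may feed into changes to the card programme, so a percentage with an unclear meaning has consequences.

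**Working it through.** No figure in the protocol needs recomputing. The check sets the card, the protocol variable and the items side by side.

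**1. Recipients.** Types of contact outside the MabThera team:

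| Contact | Card and Q12b | Section 8.3 example | Q23 and Q24 |
|---|---|---|---|
| Doctor, other condition | covered | covered | covered |
| Doctor, same condition | covered | covered | not covered |
| Nurse | covered | not covered | not covered |
| Dentist | covered | not covered, unless counted as a doctor | not covered, unless counted as a doctor |

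The items are narrower than the card in three rows. In the second row they are also narrower than the protocol's own variable.

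**2. Routing.** Q23 is the gate to Q24. A card holder whose only contacts fall in the last three rows, and who reads Q23 literally, answers No and is not asked Q24, even if the card was shown every time. A holder with mixed contacts reaches Q24 but is asked only about the first row.

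**3. Frequency.** Q24 has no all-or-some distinction. As an illustration, with values assumed and not in the document, suppose a patient sees k doctors for other conditions and shows the card to each independently with probability q. Then

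- P(shown to at least one) = 1 − (1 − q)^k
- P(shown to all) = q^k

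| q | k | at least one | all |
|---|---|---|---|
| 0.3 | 2 | 51% | 9% |
| 0.3 | 4 | 76% | 0.8% |
| 0.5 | 2 | 75% | 25% |
| 0.5 | 4 | 94% | 6% |
| 0.7 | 2 | 91% | 49% |
| 0.7 | 4 | 99% | 24% |

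A Yes at Q24 is compatible with very different degrees of adherence. The table shows what the item cannot resolve; it does not predict what the study would find.

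**4. Symptoms.** The card says doctor or nurse, straight away. Q31 offers the patient's doctor and the doctor who treated the infection. It has no nurse option. Its reference to noticing symptoms is a loose time anchor that does not separate same-day contact from contact after some delay.

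**5. Recovery at analysis.** Q31 has a free-text option for other actions, but Section 8.6 says open-ended responses will be listed and categorised, not analysed quantitatively. Q23 and Q24 have no free text. Answers that were not collected cannot be restored by an analysis plan.

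**The case against.** The strongest reply is that the protocol asks less of these items than the card does. The example in Section 8.3 is itself limited to doctors. Aim 2 asks whether the card may influence actions, not what share of patients always comply. The breadth of recipients and promptness are covered as knowledge in Q12b and Q11. Patients skipped at Q23 still reach Q29 to Q31, so any who had an infection are asked about showing the card to the treating doctor. The questionnaire is a draft, and cognitive pretesting is planned in every country.

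Part of this stands. For nurses and dentists the gap is against the card and the FUM request, not against Section 8.3. For doctors seen about the same condition, however, the items fall short of Section 8.3 as well. Knowledge items do not measure behaviour, and Q31 reaches only patients who report an infection. Draft status makes the change easy but does not ensure that pretesting, which looks for problems in understanding, would reveal a mismatch with the card.

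Three stronger readings are tempting and are not supported:

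- *The survey cannot measure use of the card at all.* Q16 and Q17 measure carrying it, Q17 on a graded scale. Q18 measures reading it, and one option in Q31 records consulting it.
- *Partial use will be reported as correct use.* Q24 and Q31 carry no correct-answer asterisk, and Section 8.6 does not score a Yes at Q24 as correct use.
- *A number of misclassified or skipped patients can be stated.* The document gives neither the share of card holders nor the mix of clinicians they see.

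**Conclusion.** The point holds for two instructions and three items. As drafted, Q23, Q24 and Q31 cannot yield the proportion of patients who show the card to any doctor, nurse or dentist, or who tell a doctor or nurse straight away. Showing the card to nurses, dentists and same-condition doctors goes unrecorded at Q24, while occasional and consistent showing are merged. The first omission can hide use and the second can make it look fuller than it is, so the net direction is unknown and the size cannot be derived from the document.

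The routing argument assumes that patients read Q23 literally. If some count a dentist as a doctor, answers become inconsistent between respondents and the gap remains. Receipt, carrying and reading of the card, and the knowledge results, are unaffected. This is worth correcting before fielding; it does not invalidate the survey.

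**What to change.** Reword three draft items before pretesting and translation.

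- **Q23:** ask about *any doctor, nurse or dentist not involved in giving or prescribing your MabThera, for any reason*. The exclusion matters. Respondents are surveyed at infusion centres, so wording that excluded only the prescriber would count infusion-centre nurses, and nearly everyone past a first infusion would pass the gate.
- **Q24:** use the same recipients, and replace Yes/No with the all, some or none of the time scale from Q17, keeping a don't-know option.
- **Q31:** change the contact option to *a doctor or nurse*, split into *straight away* and *later*. Widen the told and showed options to *the doctor, nurse or dentist who treated me*.

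Align the example of patient actions in Section 8.3 with this wording. How the answers combine into a summary of correct use can be left to the analysis plan.

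The cost is slightly longer items and some added recall burden. The recipients and the frequency scale already appear in Q12b, Q17 and Q20, so little new wording has to be tested.

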	4.2.6 Seasonality?					
4.3	Does the protocol define how the study population will be sampled from the source population? (e.g. event or inclusion/exclusion criteria)				27-30	
Comments:						

	tion 5: Exposure definition and measurement	Yes	No	N/A	Page Number(s)		
5.1	Does the protocol describe how exposure is defined and measured? (e.g. operational details for defining and categorising exposure)			\boxtimes			
5.2	Does the protocol discuss the validity of exposure measurement? (e.g. precision, accuracy, prospective ascertainment, exposure information recorded before the outcome occurred, use of validation sub-study)						
5.3	Is exposure classified according to time windows? (e.g. current user, former user, non-use)			\boxtimes			
5.4	Is exposure classified based on biological mechanism of action and taking into account the pharmacokinetics and pharmacodynamics of the drug?						
5.5	Does the protocol specify whether a dose-dependent or duration-dependent response is measured?						
Com	nments:						
This is a drug utilisation study; all participants are exposed to MabThera in the course of routine medical treatment. All patients will have received at least a MabThera infusion. Additional exposure information will be obtained from medical records. Section 6: Endpoint definition and measurement Yes No N/A Page							
	·				Number(s)		
6.1	Does the protocol describe how the endpoints are defined and measured?				32-33		
6.2	Does the protocol discuss the validity of endpoint measurement? (e.g. precision, accuracy, sensitivity, specificity, positive predictive value, prospective or retrospective ascertainment, use of validation sub-study)						
Com	nments:	,					
This is a drug utilisation study; the "endpoints" are off-label use of MabThera. Classification of these endpoints will be based on clinical indication derived from the medical record. Knowledge of the PAC will be derived from answers to the patient survey.							
Sec					or the PAC		
	tion 7: Confounders and effect modifiers	Yes	No	N/A	Page Number(s)		
7.1	tion 7: Confounders and effect modifiers Does the protocol address known confounders? (e.g. collection of data on known confounders, methods of controlling for known confounders)	Yes	No	 	Page		
7.1	Does the protocol address known confounders? (e.g. collection of data on known confounders, methods of controlling	Yes	No	N/A	Page		
7.2	Does the protocol address known confounders? (e.g. collection of data on known confounders, methods of controlling for known confounders) Does the protocol address known effect modifiers? (e.g. collection of data on known effect modifiers, anticipated	Yes	No	N/A	Page		
7.2 Com	Does the protocol address known confounders? (e.g. collection of data on known confounders, methods of controlling for known confounders) Does the protocol address known effect modifiers? (e.g. collection of data on known effect modifiers, anticipated direction of effect)	Yes	No	N/A	Page		
7.2 Com	Does the protocol address known confounders? (e.g. collection of data on known confounders, methods of controlling for known confounders) Does the protocol address known effect modifiers? (e.g. collection of data on known effect modifiers, anticipated direction of effect)	Yes	No O	N/A	Page		
7.2 Com	Does the protocol address known confounders? (e.g. collection of data on known confounders, methods of controlling for known confounders) Does the protocol address known effect modifiers? (e.g. collection of data on known effect modifiers, anticipated direction of effect) mments: is a descriptive drug utilisation study.			N/A	Page Number(s)		
7.2 Com This	Does the protocol address known confounders? (e.g. collection of data on known confounders, methods of controlling for known confounders) Does the protocol address known effect modifiers? (e.g. collection of data on known effect modifiers, anticipated direction of effect) mments: is a descriptive drug utilisation study. tion 8: Data sources Does the protocol describe the data source(s) used in the			N/A	Page Number(s)		
7.2 Com This	Does the protocol address known confounders? (e.g. collection of data on known confounders, methods of controlling for known confounders) Does the protocol address known effect modifiers? (e.g. collection of data on known effect modifiers, anticipated direction of effect) mments: is a descriptive drug utilisation study. tion 8: Data sources Does the protocol describe the data source(s) used in the study for the ascertainment of: 8.1.1 Exposure? (e.g. pharmacy dispensing, general practice	Yes		N/A	Page Number(s)		
7.2 Com This	Does the protocol address known confounders? (e.g. collection of data on known confounders, methods of controlling for known confounders) Does the protocol address known effect modifiers? (e.g. collection of data on known effect modifiers, anticipated direction of effect) ments: is a descriptive drug utilisation study. tion 8: Data sources Does the protocol describe the data source(s) used in the study for the ascertainment of: 8.1.1 Exposure? (e.g. pharmacy dispensing, general practice prescribing, claims data, self-report, face-to-face interview, etc.) 8.1.2 Endpoints? (e.g. clinical records, laboratory markers or values, claims data, self report, patient interview including scales	Yes		N/A	Page Number(s) Page Number(s) 30-35		
7.2 Com This	Does the protocol address known confounders? (e.g. collection of data on known confounders, methods of controlling for known confounders) Does the protocol address known effect modifiers? (e.g. collection of data on known effect modifiers, anticipated direction of effect) mments: is a descriptive drug utilisation study. tion 8: Data sources Does the protocol describe the data source(s) used in the study for the ascertainment of: 8.1.1 Exposure? (e.g. pharmacy dispensing, general practice prescribing, claims data, self-report, face-to-face interview, etc.) 8.1.2 Endpoints? (e.g. clinical records, laboratory markers or values, claims data, self report, patient interview including scales and questionnaires, vital statistics, etc.)	Yes		N/A	Page Number(s) Page Number(s) 30-35 30-35		

Section 8: Data sources		No	N/A	Page Number(s)		
8.2.2 Endpoints? (e.g. date of occurrence, multiple event, severity measures related to event)	\boxtimes			30-35		
8.2.3 Covariates? (e.g. age, sex, clinical and drug use history, co-morbidity, co-medications, life style, etc.)				30-35		
8.3 Is a coding system described for:						
